4.3. Recruitment, enrolment, and randomization RCT

Women will be informed about the study either at the abortion clinic (South Africa) or by phone through the collaborating abortion care hotline Reproductive Health Network Kenya (RHNK). All women in the South African arm of the study will be informed about the study while waiting to be seen for a consultation at the abortion clinics on a recruitment day. Interested women will be screened for eligibility. Eligible women will be recruited to the study after going through a private informed consent procedure with study staff.

Participants will be randomly allocated 1:1 to either TECC or in-person contraceptive counseling. The randomization sequence will be computer-generated 1:1 in permuted blocks of varying sizes by a researcher not involved in data collection and imported into the electronic research data capture tool RedCap. A research assistant will perform the randomization, in the presence of the participant on the same day as the intervention, by clicking on a link in the RedCap system which generated the next sequential number according to central allocation. Blinding of either the research assistant or participant to group allocation will not be possible.

4.4. Research procedures and data collection methods RCT

4.4.1. Research procedures and data collection methods RCT – all participants

On the day of recruitment, a baseline survey will record participant demographic variables, socio-economic status, reproductive history, prior and current use of contraception, and frequency of use of the internet. Follow up surveys will be conducted 12 weeks, 6 months, and 12 months. Baseline and follow up surveys will be recorded either by women receiving a link to RedCap and filling out the questionnaires on their phones, or through a telephonic interview with the research assistant, depending on participant preference. At baseline, data for accessing the baseline survey on RedCap and using the TECC service will be provided to participants from the study staff by means of data hotspot/WIFI provided from study staff devices. The reimbursement amount will assist participants to cover costs for data required for the follow up survey and any contact with the TECC service after baseline. The participants also have the choice to participate in follow up surveys by phone interview with study staff. The baseline survey is expected to take about 10-15 minutes. The follow up survey at 12 weeks is expected to take about 20-25 minutes and follow up surveys at 6 months and 12 months are expected to take about 5-10 minutes. The questionnaires will capture primary and secondary outcomes as described below.

Outcomes

Primary outcome at 12 weeks

Uptake of LARC, defined as uptake of an IUD or a subdermal implant for contraception, within 12 weeks

Secondary outcomes at 12 weeks

1. choice of LARC

2. uptake of any contraception
3. choice or uptake of new method with regards to previous use
4. satisfaction with TECC service (using a multi-question validated scale)
5. Rated use of service for decision making (using a multi-question validated scale)
6. Degree of agency in decision making (using a multi-question validated scale)
7. preference for counselling

Secondary outcomes at 6 months

1. continued use of LARC
2. continued use of any contraception
3. recurrent unintended pregnancy
4. recurrent abortion

Secondary outcomes at 12 months

1. continued use of LARC
2. continued use of any contraception
3. recurrent unintended pregnancy
4. recurrent abortion
5. Change of method at any timepoint up to 12 months
6. Reason for change of method

Subsidiary outcomes

We will record the following subsidiary outcomes: repeat/recurrent interaction with service, time spent on consultation

Our outcome data will be recorded and extracted as described above at 12 weeks, 6 months, and 12 months. Links for follow-up surveys on RedCap will be sent to the participants phone. Three attempts will be made to contact the participant by phone for each follow up survey in case of missing data. For participants who cannot be reached to complete missing data, clinical records on contraceptive uptake and recurrent pregnancy within 12 months will be retrieved from Cape Town electronic records and records from the clinics affiliated to RHNK in Kenya. All outcome data will be registered in the research data collection tool RedCap hosted at University of Cape Town [contact].

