Form FHS015: Research Protocol – Section C

Table of contents

- 1. Purpose of the study**
- 2. Background**
- 3. Methodology Pilot Study**
 - 3.1. Study design
 - 3.2. Characteristics of the study population
 - 3.3. Recruitment and enrolment
 - 3.4. Research procedures and data collection methods
 - 3.5. Data safety and monitoring
 - 3.6. Data analysis
- 4. Methodology RCT**
 - 4.1. Study design
 - 4.2. Characteristics of the study population
 - 4.3. Recruitment and enrolment
 - 4.4. Research procedures and data collection methods
 - 4.5. Data safety and monitoring
 - 4.6. Data analysis
- 5. Description of risks and benefits**
- 6. Informed consent process**
- 7. Privacy and confidentiality**
- 8. Reimbursement for participation**
- 9. Emergency care and insurance for research-related injuries**
- 10. What happens at the end of a study?**
- 11. References**
- 12. Appendices**

1. Purpose of the Study

This research project aims to increase access and uptake of contraception after abortion through the systematic development and testing of a new telemedicine service for contraceptive counselling (TECC). We will perform a pilot study in South Africa, and multicenter randomized controlled trial in South Africa and Kenya with the following specific aims:

1. To design and test a user-friendly online service for contraceptive counseling informed by systematic research into the preference and experience of women in our study setting.
2. To compare uptake of long-acting reversible contraception (LARC) after TECC and in-person contraceptive counseling.
3. To compare rates of choice, uptake, and continuation of LARC or any contraceptive, satisfaction, preference for counseling, recurrent unintended pregnancy, and recurrent abortion after TECC and in-person contraceptive counseling.

2. Background

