Quantitative data will be collected from a baseline survey on recruitment day and a follow-up survey after two weeks, as well as data from the TECC service itself. The baseline survey will record participant demographic variables, reproductive history, prior and current use of contraception and frequency of internet use, as well as measures of anticipated acceptability of the intervention. Information will be captured by participants themselves filling out questionnaires in Redcap after receiving a link to their phones, alternatively by being asked questions by the research assistant (depending on participant preference). At baseline, data for accessing the baseline survey on RedCap and using the TECC service will be provided to participants from the study staff by means of data hotspot/WIFI provided from study staff devices. The baseline survey is expected to take about 10-15 minutes. The follow up survey will capture choice of method after completion of TECC session as well as measures of experienced acceptability of the service in several dimensions, reason for choice of method, preference regarding timing of repeat session and challenges encountered. Data collection from the service will measure rate and time for completion of the TECC consultation session, and any points of contact between baseline and follow up. The reimbursement amount will assist participants to cover costs for data required for the follow up survey and any contact with the TECC service after baseline. The participants also have the choice to participate in follow up surveys by phone interview with study staff.

Primary outcome collected at 2 weeks

Main outcome variable will be a compound variable reflecting the proportion of women who choose a method after completing the TECC intervention and report 1) being satisfied or very satisfied with the service (affective attitude), 2) understanding the content and purpose of the intervention (coherence), 3) feeling confident in their ability to use the service (self-efficacy), experiencing the service as easy to use (burden), assessing service as likely to be of use in the community (effectiveness)

Secondary outcomes collected at 2 weeks

- 1) Contraceptive method chosen by type (%)
- 2) Choice of LARC (%), defined as choice of an IUD or a subdermal implant for contraception
- 3) Change of method with respect to previous use (%)

Subsidiary outcomes collected at 2 weeks

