4.4.3. Research procedures and data collection methods RCT – comparison group

The control group will receive in-person contraceptive counselling information and initiation at the clinic where they perform the abortion (South Africa) or a clinic to which they are directed by the abortion care hotline (Kenya). Mode of contraceptive counseling may vary between clinics but the routine procedure at each clinic will be documented in the study. To keep the study as close to clinical practice as possible we will not modify the care received by the control group by standardizing the counseling delivered at the clinics.

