4.6. Data analysis RCT

Continuous data will be presented as median (interquartile range) and dichotomous data as absolute (n) and relative (%) frequencies. Baseline data will be compared group-wise to ascertain successful randomization. Outcome data will be compared group-wise using Chi-square test according to intention to treat (ITT) among all randomized women according to allocation, and per-protocol (PP) according to the intervention women actually received. The risk ratio between groups of our main outcome and 95% confidence interval will be calculated using the STATA csi command.

Based on a previous RCT in the same setting we expect the baseline rate for our main outcome, uptake of LARC after abortion, to be 12%. We hypothesize that the intervention group using TECC will double their uptake of LARC. We also wish to be able to analyze our two study settings independently of each other. To show a doubling of uptake in a study group (effect size or odds ratio 2.0) corresponding to an absolute increase of 12%, with 95% confidence and 90% power we will need to analyze 212 women in each arm. This 95% confidence interval for that risk difference would in that case have a lower margin of 5% increase (corresponding to an OR of 1.5), which in a context of low use is considered clinically significant, i.e., the effect size of the intervention that we consider of clinical importance starts at 5%.

Based on previous studies we estimate that our loss to follow up will be up to 20% at 12 months bringing our sample to 510 women. Accounting for the statistical independency of the South African and Kenyan cohorts we double the sample for a total sample size of 1020 women of which 510 will be recruited in each country. This would give us 80% power and 95% confidence to determine a 12% difference in uptake of LARC in the intervention and control group at 12 weeks.

5. Description of Risks and Benefits

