5.2. Risk classification

We assess that the risks associated with the study intervention (i.e., online consultation for contraceptive counseling) are minimal. It is possible that the intervention is a less effective and acceptable model of care, which would primarily result in a higher rate of discontinuation and/or dissatisfaction with the service in the telemedicine arm compared to the standard care arm. This outcome of the study will be measured by the study, and potential harm to study participants will be minimized in the ways outlined below.

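### The RCT's only satisfaction outcome is defined for the TECC service alone, so it cannot support the between-arm comparison of satisfaction promised in aim 3

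*Protocol*

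**What the plan says.** Four parts of the protocol bear on how satisfaction is handled in the RCT.

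- **Aim 3 (Section 1)** is comparative. Among the results to be compared it names "satisfaction, preference for counseling, recurrent unintended pregnancy, and recurrent abortion after TECC and in-person contraceptive counseling".
- **Section 4.4.1**, which covers all participants, gives the 12-week secondary outcomes. Item 4 is "satisfaction with TECC service (using a multi-question validated scale"). No other RCT outcome at 12 weeks, 6 months or 12 months mentions satisfaction. The same section says that the questionnaires capture the outcomes as the list describes them.
- **Section 4.4.3** sets the control condition: "The control group will receive in-person contraceptive counselling information and initiation at the clinic where they perform the abortion" in South Africa, or at a clinic to which the hotline directs the woman in Kenya.
- **Section 5.2** says that a less effective and less acceptable intervention would show mainly as more discontinuation and/or more "dissatisfaction with the service in the telemedicine arm compared to the standard care arm", and continues: "This outcome of the study will be measured by the study".

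Section 4.6 adds the general rule that outcome data are compared between groups by intention to treat, "among all randomized women according to allocation".

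**The concern.** An outcome that is to be compared between randomised arms must be defined in the same way for women in both. Item 4 names the service that only the intervention arm uses. A woman allocated to in-person counselling has no TECC service to rate, so her value on item 4 is undefined. That is different from missing data, and no analysis method can supply it.

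If data collection follows the definition, the trial will end with a description of satisfaction in the TECC arm and nothing to set against it. One comparison named in aim 3 would be lost, and so would the direct measure of one of the two consequences that Section 5.2 foresees if TECC is less acceptable. The loss would be hard to repair afterwards. For women who cannot be reached, Section 4.4.1 falls back on clinical records, but only for contraceptive uptake and recurrent pregnancy. Satisfaction can be obtained only by asking.

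**Working it through.** The point rests on definitions, so the check is to set the passages side by side. The only arithmetic concerns who is affected.

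**1. What is to be compared, and what is defined**

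| Place in protocol | What satisfaction refers to | Arms covered |
|---|---|---|
| Section 1, aim 3 | Satisfaction after either form of counselling | Both |
| Section 5.2 | Dissatisfaction, telemedicine against standard care | Both |
| Section 4.4.1, item 4 | Satisfaction with the TECC service | TECC only |

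**2. Can a control woman have a value on item 4?** Section 4.4.3 gives her in-person counselling. Section 5.3 provides for cross-over in one direction only: a woman who cannot complete the online session moves to standard counselling. No route by which a control woman would use TECC is described. The answer is no.

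**3. Does another listed outcome fill the gap?**

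- Item 7, preference for counselling, is named separately from satisfaction in aim 3, so the protocol itself treats it as something else.
- Item 6, agency in decision making, and continued use at 6 and 12 months can be measured in both arms but are different constructs.
- Item 5, "Rated use of service for decision making (using a multi-question validated scale"), concerns decision making. It does not name TECC. It is unclear whether its word for the service covers in-person counselling.

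None of these measures satisfaction with in-person counselling.

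**4. How many women are outside the definition?** Section 4.2 plans 510 women per country, and Section 4.3 allocates 1:1.

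- Total: 510 + 510 = 1020.
- Control arm: 1020 / 2 = 510.
- Per country: 510 / 2 = 255.

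These are planned numbers before loss to follow-up. They give the size of the arm with no defined value; they do not measure bias or lost power.

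**5. Share of the outcome list.** Of the seven secondary outcomes at 12 weeks, one (item 4) is worded for TECC only, and one (item 5) is ambiguous.

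**6. Contrast with the pilot.** The pilot's compound outcome in Section 3.4 includes "being satisfied or very satisfied with the service (affective attitude"). There the wording does no harm, because the pilot has one arm and the intervention is given to every participant. A two-arm trial needs a term that applies to both arms.

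**The case against.** The strongest reply is that this is a slip in a label. Aim 3 states the comparison outright, item 4 stands in a section written for all participants, and every participant receives the 12-week survey. The intention can be recovered, and data are lost only if one label is followed literally against the stated aim. The RCT follow-up interview, listed in Section 12 but not shown, may already ask both arms a parallel question. This is fair as to consequence: whether control data will actually be missing cannot be settled from the protocol. It does not rescue the definition, because Section 4.4.1 says that the questionnaires follow the outcome list.

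Two supporting points are also weaker than aim 3. Section 5.2 speaks of discontinuation and/or dissatisfaction, so measuring continuation could be argued to meet it in part. The sentence in Section 4.6 is general, and the subsidiary outcomes include use of the service, which also looks specific to one arm; that sentence alone does not show that every listed item was meant to have a control value. Both reservations stand, and the conclusion rests mainly on Section 4.4.1 against aim 3.

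Finally, the validated scale is not named. If it was built for digital services, rewording the outcome would not make it suitable for in-person counselling, and women who cross over need a rule. Both points affect the remedy and are taken up there.

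**Conclusion.** The concern holds. As the protocol defines it, the only RCT satisfaction outcome exists in one arm, and the comparison in aim 3 cannot be made from it. This is an inconsistency in what the protocol states, not a detail that a statistical analysis plan could supply: an analysis plan cannot create control responses that were never collected.

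The size is limited. One of seven 12-week secondary outcomes is affected, with no defined value for the 510 planned control women. The ambiguity in item 5 is a matter for clarification and would not be a finding alone. The primary outcome, LARC uptake within 12 weeks, and the sample size are untouched, and other signals of acceptability remain comparable between arms.

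The conclusion assumes that the outcome list is read as written and that control women do not use TECC. Confidence in the mismatch of wording is high. Whether it would lead to an actual loss of data depends on a questionnaire that is not at hand. The correction should be made because a stated aim depends on it.

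**What to change.** - Redefine item 4 as satisfaction with the contraceptive counselling received, measured at the 12-week survey with the same scale and the same wording in both arms.
- Name the scale, and confirm that it suits both online and in-person counselling. If the intended scale applies only to digital services, choose one that does not depend on the mode of delivery.
- State that the comparison is by allocation. A woman allocated to TECC who crosses over rates the counselling she actually received and is counted in the TECC arm under intention to treat.
- Keep any questions specific to TECC as descriptive results for the intervention arm.
- State that item 5 refers to the counselling received in either arm.
- Check the draft RCT follow-up interview against the revised wording.

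The cost is a wording change to one outcome, a clarification of another, and at most a few neutral items or a substitute scale in a survey already planned for all participants. It needs no extra visits and no extra women.

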4.4.2. Research procedures and data collection methods RCT – Intervention group

The intervention will consist of online contraceptive counseling - TECC. On the day of the abortion, while waiting for their abortion consultation with the clinic nurse, participants will use their phones to complete a contraceptive counseling session through the TECC service. At baseline, data for using the TECC service will be provided to participants from the study staff by means of data hotspot/WIFI provided from study staff devices.

Participants will be informed and guided to their method of choice based on their reported preferences, reproductive history, and health conditions. The TECC will be designed to be interactive, i.e., provide a personalized path through contraceptive counseling the content of which depends on the individual needs and preferences of the participant.

After completing a counseling session, participants in the TECC group will receive an online medical certificate certifying that she has received professional contraceptive counseling and, if no contraindications to use exist, that she's eligible for the method of

her choice. If she has a medical condition that requires examination prior to prescription her certificate will indicate that she must see a nurse prior to initiation of her method. Depending on her choice, she will then be directed with this certificate to the nearest clinic for initiation of the method (intrauterine device, progestin injectable, or progestin implant), or to a pharmacy to pick up her method (progestin-only pill, combined oral contraceptive pill. In Kenya, women will receive home distribution or distribution to a local pick-up point, through our partner organization and distributor of contraceptives Triggerise.org. A question in the TECC chat will allow participants to ask the TECC backoffice (study doctor) to contact them for further support. The chat algorithm will also automatically alert the study doctor in case of a severe liver disease or cancer, which would require further attention.

After a period of time (expected to be 8-10 weeks after the abortion and to be determined by an ongoing study and the pilot study leading up to this trial), women will be contacted through the service and offered the opportunity to go through the screening and information session again to confirm, or reconsider, their method of choice. Based on our previous research, we expect many women will leave the abortion clinic with the 3-months progestin injectable as contraceptive method. A second counseling session will allow them to reconsider their method of choice before the next planned injection. The TECC service will send three supportive messages or nudges during the first three months to remind women to initiate their chosen method and offer them support or a renewed counseling session if they are not content with their previous choice of method.

4.4.3. Research procedures and data collection methods RCT – comparison group

The control group will receive in-person contraceptive counselling information and initiation at the clinic where they perform the abortion (South Africa) or a clinic to which they are directed by the abortion care hotline (Kenya). Mode of contraceptive counseling may vary between clinics but the routine procedure at each clinic will be documented in the study. To keep the study as close to clinical practice as possible we will not modify the care received by the control group by standardizing the counseling delivered at the clinics.

4.5. Data safety and monitoring RCT

The accuracy and reliability of the data collected will be periodically validated during the study. The research assistants will be trained in how to use the study questionnaires in a standardized way. The two principal investigators will continuously for the first three months of the study, and then periodically, supervise study procedures at the study sites.

Study staff from the DSBS will also conduct periodic quality controls of the data and ensure that the data are being collected in accordance with both South African and international ethical guidelines. This will include review of:

1. Essential documents file (Initiation letter, CVs, training records, agreements, etc.),
2. All ethics committee approvals and communication,
3. Data collection methods (via observation),

4. Blank data collection and consent materials (for version control),
5. Completed CRFs (to ensure adherence to GCP),
6. All completed consent forms and link logs,
7. Source documents,
8. Storage facilities for data,
9. Study product inventory and storage facilities,
10. Protocol deviations,
11. Adverse and serious adverse events logs and reports, and
12. Any other documents as needed.

A co-investigator and consultant to the trial will act as monitor to the trial and perform periodic assessments of the validity and consistency of data collection.

A data and safety monitoring board (DSMB) will be formed for the study. The DSMB will review adverse outcomes at an interim stage of the study (after 6 months) but will not a priori perform an interim data analysis. This is because we 1) do not expect the intervention to put the participant at increased risk of severe adverse events, and 2) that the intervention would differ from standard care to an extent that would require early closure of the study.

